- **Cohort 1:** If none or only 1 subject experienced a DLT, initiate enrollment in Cohort 2. If 2 or more subjects experienced a DLT, initiate enrollment in Cohort -1.
- **Cohort -1:** If none or only 1 subject experienced a DLT, the doses used in Cohort -1 will be considered the RP2D. If 2 or more subjects experienced a DLT, the combination of H3B-6545 and palbociclib at clinically meaningful doses will be considered unfeasible.
- **Cohort 2:** If none or only 1 subject experienced a DLT, initiate enrollment in Cohort 3. If 2 or more subjects experienced a DLT, the doses used in Cohort 1 will be considered the MTD and the RP2D.
- **Cohort 3:** If none or only 1 subject experienced a DLT, doses used in this Cohort will be considered the RP2D. If 2 or more subjects experienced a DLT, consideration will be given to opening cohort 3b depending upon observed toxicity profile.
- **Cohort 3b:** If none or only 1 subject experienced a DLT, doses used in this Cohort and in Cohort 2 could be considered the RP2D. In this case, the SRC will select between Cohort 2 and Cohort 3b for the expansion phase. If 2 or more subjects experienced a DLT, doses used in Cohort 2 will be considered the RP2D.

The MTD is defined as the highest dose at which no more than 1 of 6 subjects experiences a DLT in the dose cohort. The RP2D may not exceed the MTD and will be agreed upon by the SRC based on an integrated evaluation of available safety, clinical benefit, PK, and pharmacodynamics data, for all dose levels tested.

DLTs: Unless considered not related to study drugs, any of the following criteria will qualify as a DLT:

Toxicity	Criteria ^a	
Hematology	- Febrile neutropenia (ANC <1×10 ⁹ /L and fever \ge 38.5 ° C)	
	- Grade 4 neutropenia that does not resolve to Grade ≤ 2 (ANC $\geq 1 \times 10^{9}/L$) within 7 days; use of GM-CSF is allowed	
	- Grade 4 thrombocytopenia (<25.0×10 ⁹ /L)	
	 Grade 3 thrombocytopenia (25.0 – 50.0×10⁹/L) lasting more than 7 days or associated with clinically significant bleeding 	
Vomiting	- CTCAE Grade 4 vomiting	
	- Grade 3 vomiting lasting >72 hours despite optimal antiemetic treatment	
Diarrhea	- CTCAE Grade 4 diarrhea	
	- Grade 3 diarrhea lasting >72 hours despite optimal antidiarrheal treatment	

Electrolytes abnormality	 Grade 4 Grade 3 lasting for more than 24 hours Note: Grade 3 that lasts <24 hours and resolves spontaneously or responds to conventional medical interventions is not considered a DLT. 	
Renal	- Grade 3 or 4 serum creatinine	

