- The current cohort so that the total number of DLT-evaluable subjects is maintained at 6, if any of the 6 already dosed subjects becomes non-evaluable for DLT;
- A lower dose cohort which has already been deemed safe per dose escalation meeting, if none of the 6 already dosed subjects becomes non-evaluable for DLT in the cohort currently under evaluation; the additional subject(s) will not contribute to DLT evaluation of the lower dose cohort, but will contribute to the overall safety evaluation.
- The next cohort to be opened to enrollment including the expansion cohort if the RP2D has been reached and the expansion phase is open to enrollment.

Sponsor approval of any enrollment scenario not described above must take place prior to screened subject enrollment.

In the 1st cycle, palbociclib will be administered PO QD on Days 1 to 21 and H3B-6545 will be administered PO QD on Days 9 to 28. In all subsequent cycles, palbociclib will be administered on Days 1 to 21 and H3B-6545 will be administered Days 1 to 28.

A maximum of 4 dose levels are planned, with palbociclib escalated no higher than 125 mg QD and H3B-6545 escalated no higher than 450 mg QD (RP2D); see dose escalation in Table 3.

Dose Level (Cohort)	Palbociclib Dose (mg QD)	H3B-6545 Dose (mg QD)	Number of DLT- Evaluable Subjects
-1	75	300	6
1 (starting dose)	100	300	6
2	125	300	6
3	125	450	6
3b	100	450	6

Table 3Dose Escalation

DLT = dose limiting toxicity; QD = once daily.

Subjects will be assigned to a dose level in the order of study entry. DLTs will be assessed during the first 28 days starting from the 1st day of adding H3B-6545 to palbociclib (Cycle 1 Day 9 to Cycle 2 Day 8). Subjects who do not receive at least 75% of the scheduled therapy

from Cycle 1 Day 9 to Cycle 2 Day 8, for reasons other than toxicity, will not be considered evaluable for DLT assessment and will be replaced. Disease progression and AEs deemed related to disease progression will not be considered DLTs.

After all subjects in a cohort have completed the DLT observation period, all available safety data will be reviewed by the Safety Review Committee (SRC) consisting of sponsor personnel and investigators, and the decision to proceed to the next dose cohort will be made jointly.

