3.2 Overall Study Design and Plan

H3B-6545-G000-102 is a multicenter, open-label study of H3B-6545 in combination with palbociclib for women with advanced or metastatic ER+ HER2- breast cancer. This study consists of 2 parts: dose escalation (Part 1) and dose expansion (Part 2). Subjects in dose escalation must have progressed after 2 prior endocrine therapies and may have received up to 1 prior chemotherapy regimen and up to 1 prior CDK4/6 inhibitor. Subjects in dose expansion may have received up to 2 prior endocrine therapies and up to 1 prior chemotherapy regimen, but may not have received a prior CDK4/6 inhibitor in the advanced or metastatic setting.

Eisai Confidential Page 7 of 30

Treatment cycles will begin with the first dose of palbociclib in Cycle 1 administered orally (PO) once daily (QD) on Days 1 to 21 and H3B-6545 administered PO QD on Days 9 to 28. In all subsequent cycles, palbociclib will be administered on Days 1 to 21 and H3B-6545 will be administered Days 1 to 28. Intrasubject dose escalation is allowed (Section 9.1, Protocol version 5.0, Amendment 4.0). Treatment will continue until disease progression, development of unacceptable toxicity, or withdrawal of consent.

Safety assessments will be collected up to 28 days after last treatment administration, and include adverse events (AEs) (graded by Common Terminology Criteria for Adverse Events [CTCAE] v5.0), laboratory, vital signs, electrocardiogram (ECG) and physical examinations. Tumor assessments will be performed every 8 weeks (± 1 week) according to Response Evaluation Criteria in Solid Tumors (RECIST) 1.1 (Eisenhauer et al., 2009) and based on investigator assessment, until documented disease progression or starting another anticancer therapy. All subjects will be followed for survival approximately every 3 months, and survival follow-up will end 6 months after the last subject receives their first dose of study treatment (at the time of data cutoff for the primary analysis) (as of Amendment 4.0), and no survival follow-up will be done in the Extension Phase. Detailed schedule of procedures and assessments are included in Table 8 of the Protocol (version 5.0, Amendment 4.0).

The data cutoff date for the primary analysis will be approximately 6 months after the last subject of the Dose Escalation Part receives their first dose of study treatment. There will be no subjects enrolled for the Dose Expansion Part.

Dose Escalation Part

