4 DETERMINATION OF SAMPLE SIZE

Depending on the dose levels to be studied in the dose escalation phase, approximately 12 to 24 subjects may be treated. Dose expansion will enroll 12 additional subjects at the RP2D. Therefore, the study is expected to enroll approximately 24 to 36 subjects. No formal sample size calculation is performed.

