5.6 Safety Analyses

The determination of the MTD and/or RP2D will be based on Dose Evaluable Set that consists of all DLT-evaluable subjects. Subjects not evaluable for DLT assessment will be replaced.

All other safety analyses will be performed on the Safety Analysis Set. Safety data will be summarized on an "as treated" basis using descriptive statistics (eg, n, mean, SD, median, minimum, maximum for continuous variables; numbers and percentages (n [%]) for categorical variables). Safety variables include treatment-emergent adverse events (TEAEs), clinical laboratory parameters, vital signs, and 12-lead ECG results.

Study Day 1 for all safety analyses is defined as the date of the first dose of study drug (H3B-6545 or Palbociclib, whichever is earlier). Safety summary will include post-baseline data during the treatment period (starting from first dose date of study drug to last dose date of study drug + 28 days).

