5.6.3 Adverse Events

The AEs will be collected for each subject until 28 days after last study drug administration. The NCI CTCAE v5.0 will be used for AE grading.

The AE verbatim descriptions (investigator terms from the CRF) will be classified into standardized medical terminology using MedDRA. The AEs will be coded to the MedDRA (Version 22.1 or higher) lower level term closest to the verbatim term. The linked MedDRA PT and primary system organ class (SOC) are also captured in the database.

A TEAE is defined as the following:

- an AE that emerges during treatment (from first dose of study drug up to 28 days after last dose), having been absent at pretreatment (Baseline) or
- an AE that reemerges during treatment, having been present at pretreatment (Baseline) but stopped before treatment, or
- an AE that worsens in severity during treatment relative to the pretreatment state, when the AE is continuous.

The AEs will be summarized using the Safety Analysis Set. Only those AEs that are treatment-emergent will be included in summary tables. The incidence of TEAEs will be reported as the number (percentage) of subjects with TEAEs by SOC and PT. A subject will be counted only once within an SOC and PT, even if the subject experienced more than 1 TEAE within a specific SOC and PT. The number (percentage) of subjects with TEAEs will also be summarized by maximum CTCAE grade, or by relationship to study drug (Yes

Eisai Confidential Page 17 of 30

[means related to H3B-6545 or palbociclib or both] and No [means not related to either H3B-6545 or palbociclib]).

Number (percentage) of subjects will be summarized by treatment groups in the following analysis:

- Overview of TEAEs (including TEAEs, TEAEs by maximum grade, TEAEs by relationship, treatment-emergent SAEs, treatment-related TEAEs, TEAEs leading to study drug discontinuation, TEAEs with Grade ≥ 3, TEAEs leading to study drug reduction, TEAEs leading to study drug interruption, and TEAEs leading to death)
- TEAEs by SOC and PT
- TEAEs by SOC, PT and maximum grade
- TEAEs by PT in decreasing frequency
- TEAEs of Grade ≥3 by SOC and PT
- Treatment-related TEAEs by SOC and PT
- Treatment-related TEAEs by SOC, PT, and maximum grade
- Treatment-related TEAEs of Grade ≥3 by SOC and PT
- Treatment-emergent SAEs by SOC and PT
- Treatment-emergent SAEs by SOC, PT, and maximum grade
- Treatment related treatment-emergent SAEs by SOC and PT
- TEAEs leading to study drug discontinuation by SOC and PT

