5.6.4 Laboratory Values

Laboratory results will be summarized by treatment groups on the Safety Analysis Set. The analysis will include assessment collected at baseline and/or during treatment (from first dose to 28 days after last dose date), using Système International (SI) units, as appropriate. Values that are non-missing and reported as 'below the detectable limit' of an assay will be replaced by half of the detectable limit in the summary tables.

For all quantitative parameters, the numeric value and the change from baseline to each post-baseline visit (including end of treatment visit and safety follow up visit) will be summarized by visit using descriptive statistics. Qualitative parameters summarized by frequencies (number and percentage of subjects) at each post-baseline visit (including end-of-treatment visit and safety follow up visit) will be reported.

Furthermore, the frequency of laboratory abnormalities by maximum post-baseline CTCAE grade will be summarized for selected laboratory parameters, including hemoglobin, White Blood Cell Count (WBC), Absolute neutrophil count (ANC), lymphocytes, platelet count, alkaline phosphatase (ALP), aspartate aminotransferase (AST), alanine aminotransferase (ALT), bilirubin, creatinine, estimated glomerular filtration rate (eGFR) calculated using the MDRD formula, thyroid stimulating hormone (TSH) and electrolytes. Shift tables will also be produced for selected parameters based on the baseline CTCAE grade and the maximum CTCAE grade at post-baseline visits.

Listings of laboratory results will be provided. In addition, a listing of potential Hy's law cases will be provided, including subjects who meets one of the following criteria at any post-baseline timepoint (not necessarily at the same timepoint): AST or ALT >3 x upper limit of normal (ULN). Parameters (AST, ALT, Total Bilirubin, ALP as multiples of ULN) at all timepoints will be included. Subjects meeting Hy's Law definition will be discussed in the clinical study report based on *FDA Guidance for Industry Drug Induced Liver Injury: Premarketing Clinical Evaluations* (2009).

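### Cohorts open in sequence but share one cutoff, so whole-period TEAE and worst-grade percentages tend to run higher in earlier-opened cohorts; SAP 5.6 needs a common-window comparison by dose

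*SAP*

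**What the plan says.** - **Order of enrolment.** Protocol 9.1: "Subjects will be assigned to a dose level in the order of study entry". The Protocol synopsis makes each step conditional on the cohort before it; for Cohort 1, "If none or only 1 subject experienced a DLT, initiate enrollment in Cohort 2". The Safety Review Committee meets once a cohort has completed its DLT window.
- **One cutoff.** SAP 3.2 places the primary analysis cutoff "approximately 6 months after the last subject of the Dose Escalation Part receives their first dose of study treatment". The same section says that nobody will be enrolled in the expansion part, and that treatment runs until progression, unacceptable toxicity or withdrawal of consent.
- **Safety window.** SAP 5.6: "Safety summary will include post-baseline data during the treatment period (starting from first dose date of study drug to last dose date", with 28 days added.
- **Statistics.** For TEAEs, SAP 5.6.3 has "Number (percentage) of subjects will be summarized by treatment groups in the following analysis". For laboratory data, SAP 5.6.4 tabulates "the frequency of laboratory abnormalities by maximum post-baseline CTCAE grade". SAP 5.6.5 and 5.6.6 classify vital signs and ECGs by the worst post-baseline result.
- **Exposure.** SAP 5.6.1 summarises treatment duration, total dose and dose intensity by drug. It does not say that this is split by treatment group, and it does not link exposure to the event rates.
- **Escalated subjects.** Protocol 9.1 allows intrasubject escalation once Cycle 3 is complete. SAP 5.6 reports on an as-treated basis but does not say which treatment group such a subject belongs to.

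**The concern.** The percentage of subjects who ever had an event, or whose worst grade reached a threshold, can only rise with observation time. If one dose cohort can be observed for a year and another for six months, the first will tend to show more events even when the drugs are equally toxic at both doses. SAP 5.6 has no common-window table, time-to-first-event summary or exposure-adjusted rate for TEAEs or worst values. If duration is not shown by cohort, a reader of the tables may not see the imbalance.

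The stake is the descriptive comparison of doses. With no expansion part, the escalation tables are the study's only by-dose safety record. Both documents base the RP2D on an integrated view of safety, benefit, PK and pharmacodynamics at all dose levels. If Cohort 3b passes its DLT rule, the committee must choose between Cohorts 2 and 3b, which both passed, so safety data beyond DLTs would matter.

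**Working it through.** The plan gives no figure to reproduce: SAP 4 states "No formal sample size calculation is performed". The check asks how far the percentages differ between cohorts when the true hazard is the same at every dose.

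**Inputs**
- First dose to Cycle 2 Day 8 is about 36 days (28 + 8; Protocol 9.1). Two steps take at least 2 × 36 / 30.4375 = 2.4 months before any accrual or review time.
- Assumed: 30 to 60 days of accrual per cohort. Three later cohorts then take 3 × (66 to 96) days = 198 to 288 days, or 6.5 to 9.5 months. I use gaps of 6 and 9 months, so potential follow-up is T = 12 or 15 months against 6 for the last subject.
- Assumed: time on treatment is exponential with median 5.3 months, the monotherapy median PFS in Protocol 7.2.1. This gives h = ln 2 / 5.3 = 0.1308 per month.
- Assumed: constant event hazard l of 0.05 or 0.10 per month.

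**Formulas**
- Mean time on treatment = (1 − e^(−hT)) / h
- Proportion ever affected = l / (l + h) × (1 − e^(−(l + h)T))

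| | T = 6 | T = 12 | T = 15 |
|---|---|---|---|
| Mean months on treatment | 4.16 | 6.05 | 6.57 |
| l = 0.05 | 18.3% | 24.5% | 25.8% |
| l = 0.10 | 32.5% | 40.6% | 42.0% |

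The differences from T = 6 are 6.2 and 7.5 points at l = 0.05, and 8.1 and 9.5 points at l = 0.10. One subject in six is 16.7 points.

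**Sensitivity.** A simulation (400,000 subjects per scenario) added the 28-day tail and varied the gap over 2.4, 6 and 12 months. Results are for the last subject against an early-cohort subject.
- Median 5.3 months, 0.10 per month: 36.1% against 41.3%, 45.2% and 47.6% (5.2 to 11.5 points).
- Median 5.3 months, 0.03 per month: 12.9% against 15.4%, 17.8% and 19.7%.
- Median 5.3 months, front-loaded events (0.3 per month for two months, then 0.03): 48.0% against 49.5%, 50.9% and 52.0% (ratios 1.03 to 1.08).
- Median 10 months (assumed), 0.10 per month: 39.9% against 54.4% at a 6-month gap and 59.6% at 12 months. The last difference, 19.7 points, is the only kind of case here that exceeds one subject in six.

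**Candidate remedies**
- A window that every subject could complete before the cutoff gives a ratio of 1.00 by construction when hazards are equal.
- Events per subject-month give 1.00 only if the hazard is constant. With the front-loaded pattern, median 5.3 months and no tail, mean time within the first two months is (1 − e^(−2h)) / h = 1.76 months.
  - T = 6: events per subject = 0.3 × 1.76 + 0.03 × (4.16 − 1.76) = 0.600; rate = 0.600 / 4.16 = 0.144 per month.
  - T = 12: events per subject = 0.528 + 0.03 × (6.05 − 1.76) = 0.657; rate = 0.657 / 6.05 = 0.109 per month.
  - The ratio is about 0.75, so the longer-followed cohort looks safer although nothing differs.
- Cycles 1-2 end at Day 56. Intrasubject escalation cannot begin before Cycle 3 is complete (Day 84, week 12). The Cycles 1-2 window is therefore free of escalated dosing, and a 24-week window is not.

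**The case against.** The strongest reply is that the plan already protects what matters most. The DLT table uses the same 28 days in every cohort. Laboratory values, vital signs and ECGs are also tabulated by scheduled visit, so doses can be compared at the same cycle. The study tests no hypothesis. The best-known palbociclib toxicity comes early: Protocol 9.5 gives neutropenia in 80% to 83% of patients with a median onset of 15 days, and front-loaded events show ratios of only 1.03 to 1.08. The 6-month figure applies only to the last subject, so a comparison of cohort averages would show less. All of this stands, and it limits the point to the TEAE and worst-value tables.

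Three stronger readings are tempting, and the documents do not support them.
- **A reader might infer that the thinner visit schedule adds to the inflation.** Protocol Table 8 reduces blood counts and vital signs to Day 1 from Cycle 3, and ECGs to Day 1 from Cycle 2, identically in every cohort. Fewer late visits mean fewer late detections in long-followed subjects. With an assumed 2% chance of detection per blood count and a 6-month gap, the difference is 3.6 points on the actual schedule and about 8 points had visits stayed dense. Thinning shrinks the gap, and AEs are recorded throughout.
- **A reader might infer that the lower doses are always the ones inflated.** That fits only the path from Cohort 1 to 2 to 3. Cohort -1 would open after Cohort 1, Cohort 3b after Cohort 3, and Protocol 9.1 lets surplus subjects join a lower cohort late. The distortion follows opening order.
- **A reader might infer that the MTD or the RP2D decision is biased.** The MTD uses the fixed window. The committee meets after each cohort's DLT window, and no passage ties its decision to the final tables.

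**Conclusion.** The concern holds for the descriptive by-dose tables of TEAEs and of worst laboratory, vital-sign and ECG categories. Earlier-opened cohorts tend to show higher percentages at equal hazard. The size is about 6 to 9 points under a constant hazard of 5 to 10% per month, a 5.3-month median on treatment and a 6 to 9 month gap. It is less for early-onset events. It would be more if treatment lasted much longer or the gap approached a year. The hazards, accrual times and treatment duration are assumptions; the documents do not report actual exposure by cohort.

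It would go too far to say that the tables mask a true dose-toxicity gradient. At six subjects per cohort the expected shift is under one subject, so sampling error dominates. The distortion can blur the comparison, but it is systematic and cheap to remove, which makes the change worth making.

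**What to change.** In SAP 5.6:
1. Add tables by initial dose, limited to Cycles 1-2, as the main cross-dose comparison. They should cover TEAEs, Grade ≥3 TEAEs, worst laboratory, QTcF and heart-rate categories, and dose reductions and interruptions.
2. Add the same tables for the first 24 weeks, which fits the roughly 6-month minimum follow-up. Censor data after an intrasubject escalation or show them separately, and state the rule.
3. Report duration of treatment and subject-months by cohort.
4. Keep the whole-period tables as supportive. Any events per subject-month should also be supportive only, because they over-correct when events are front-loaded.

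The cost is SAP wording and a date cut on existing tables; no new data are needed. The downside is a few extra tables, and late-onset events would appear only in the supportive ones.

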5.6.1 Extent of Exposure

Exposure will be summarized descriptively by drugs for the Safety Analysis Set, including the following parameters defined per subject:

• Duration of treatment (in months), defined as (date of last dose – date of first dose +1)/30.4375, regardless of drug interruptions.

Eisai Confidential Page 16 of 30

- Total dose received (mg) by drug (H3B-6545, or palbociclib)
- Actual Dose Intensity (ADI, mg/day) by drug (H3B-6545, or palbociclib): total dose received (mg)/duration of treatment (days).

In addition, number of patients with dose reduction and dose interruption will be summarized.

A dose reduction of H3B-6545 or palbociclib (respectively) refers to the situation when the administration of H3B-6545 or palbociclib (respectively) was reduced 1 level lower. For H3B-6545, dose interruptions are identified by 0 doses, which are preceded and followed by the same dose level. If the dose after the 0 dose is lower than that before the 0 dose, this dose change will be counted as a dose reduction.

A by-patient listing of the date of study drug administration and the dose administered will be presented. Patients experiencing any dose modification (eg, increase, reduction, or interruption), together with the reasons for dose modification, will also be provided in a separate listing.

5.6.2 Dose Limiting Toxicity Data

In the Dose-Evaluable Set, the number (percentage) of subjects with DLTs will be presented by treatment groups. A listing of subjects with DLTs will be provided.

